## 9. INTERIM ANALYSIS AND DATA MONITORING COMMITTEE REVIEW

There will be no interim read performed on this study.

## 10. SUBJECT INFORMATION

### 10.1. Disposition Information

Enrolled subjects will be allocated to one of the three mutually exclusive:

1. Completed: Subjects are considered to have completed the study if they (a) provided informed consent and/or assent; (b) they are eligible; (c) completed all three phases of testing; and (d) have not withdrawn/discontinued from the study.

2. Discontinued: Subjects are considered to have discontinued from the study if (i) test article was administered and (ii) discontinued from the study. Reasons for discontinuation include: (a) Adverse Event (b) unsatisfactory visual response due to test article (c) satisfaction lens fitting due to test article (d) lens discomfort (e) lens handling difficulties (e) withdrew consent during study (f) lost to follow-up (g) subject no longer meets eligibility criteria (h) subject withdrawn by PI to non-compliance to protocol (i) test article no longer available
3. Assigned and Test Article Administered: Total number subjects for which test articles were administered (Completed + Discontinued).
4. Enrolled but Not Dispensed: Subjects are considered to be Enrolled Not Dispensed Subjects if they were (i) enrolled to the study (provided informed consent and/or assent) but failed to satisfy the eligibility criteria (inclusion/exclusion criteria) or (ii) if they are randomized but did not receive a test article.
5. Total enrolled: Completed + Discontinued + Enrolled but Not Dispensed.

## **10.2. Protocol Deviations**

Any protocol deviation that could impact the primary endpoints will result in the subject being excluded from the Per-Protocol analysis population. No analysis on protocol deviations will be performed. All reported protocol deviations will be listed.

## **10.3. Demographics and Baseline Characteristics**

Demographic characteristics will be summarized by Per-Protocol, safety, and all enrolled population by strata (myopes and hyperopes) using descriptive statistics for continuous variables, and numbers and percentages of subjects for categorical variables. Demographic information will include age, gender, race, ethnicity and ADD power.

## **10.4. Treatment Compliance and Extent of Exposure**

Average daily wear time and average daily comfort wear time will be provided in the summary table. Non-compliance will be reported in protocol deviation.

## **10.5. Prior and Concomitant Medications**

Prior and concomitant medications will be documented during screening and updated during the study when applicable. A listing for both prior and concomitant medications will be created for all enrolled subjects.

Disallowed medications for this study include: Anticholinergics, Oral Phenothiazines, Oral Retinoids, Corticosteroids and Oral Tetracycline.

Concomitant therapies that are disallowed include: Not applicable.

## 10.6. Medical History

A listing of medical and surgical history will be created for all enrolled subjects.

## 11. STATISTICAL ANALYSIS

### 11.1. Primary Analysis

#### Primary Safety Analyses

##### **Strategy of Incorporating Historical Data:**

Safety analysis will be performed by incorporating of historical data from studies: [REDACTED]

[REDACTED] All these studies evaluated the same Test lens that was built in different manufacturing platforms to the same in vitro product requirements and are also considered to be representative of final commercial production. The historical individual data will be incorporated using is the power prior distribution (Ibrahim and Chen; 2000).

Let  $(y, z)$  and  $(y_0, z_0)$  denote the data from current study, and from historical data respectively,  $p$  the proportion of eyes with response 1 and  $\rho$  the correlation between left and right eyes. To construct a power prior distribution for parameter of interests  $(p, \rho)$ , we use the formula

$$P(p, \rho | y_0, z_0, a_0) \propto L(p, \rho | y_0, z_0)^{a_0} \pi_0(p, \rho),$$

where  $L(p, \rho | y_0, z_0) \propto P(y_0, z_0 | p, \rho)$  is the likelihood of  $(p, \rho)$  based on the historical data and  $a_0$  is a discounting parameter constrained between 0 and 1. This parameter  $a_0$  controls the amount of the historical data we are borrowing:  $a_0 = 0$  corresponds to no incorporation of the historical data, while  $a_0 = 1$  corresponds to full borrowing of historical data. We set  $a_0 = 0.30$  for historical data of the Test lens was made in FMP and TAM21 platforms and  $a_0 = 0.10$  for Test lens made in the pilot line.

The posterior distribution of  $(p, \rho)$  given the current and historical data is

$$P(p, \rho | y, z, y_0, z_0, a_0) \propto L(p, \rho | y, z) L(p, \rho | y_0, z_0)^{a_0} \pi_0(p, \rho),$$

where  $L(p, \rho | y, z) \propto P(y, z | p, \rho)$  is the likelihood of  $(p, \rho)$  based on the current data.

#### **Primary Safety Analyses:**

Slit lamp finding grade 3 or higher and unacceptable lens fitting responses (yes/no) will be analyzed separately on the safety population using the Bayesian model described below. A sensitivity analysis will be conducted with no borrowing of historical data.

#### **The Model:**

Let  $Y_1$  and  $Y_2$  denote the binary outcomes for the left and right eyes, respectively, when wearing the test lens. Considering the correlation,  $\rho$ , between  $Y_1$  and  $Y_2$ , the distribution of the CR-6400, Statistical Analysis Plan Version 1.0

sum  $Y = Y_1 + Y_2$  is obtained by the mixture of two variables. One of them follow a binomial distribution  $\text{Bin}(2, p)$  with mixing probability  $(1-\rho)$  and the other one follows a modified Bernoulli distribution  $\text{MBern}(p)$ , taking value 0 and 2 rather than conventional 0 and 1, with mixing probability  $p$ :

$$P(Y = y | p, \rho) = (1 - \rho)\text{Bin}(2, p)I_{A1} + \rho\text{MBern}(p)I_{A2};$$

where  $I_{A1} = \{0, 1, 2\}$  and  $I_{A2} = \{0, 2\}$

To overcome the complexity of the mixture likelihood a latent variable  $Z_i$ ,  $i = 1, 2$  is introduced in the model to indicate in which component of the model the observation  $y_i$ ,  $i=1, 2$ , belongs to, that is,

$$z_i = \begin{cases} 1, & \text{if the observation belong to the } \text{MBern}(p), \\ 0, & \text{if the observation belong to the } \text{Bin}(2, p) \end{cases}$$

The joint distribution of the augmented data  $(Y_i, Z_i)$ ,  $i=1, 2$ , is given by

$$P(Y = y_i, Z = z_i | p, \rho) = \rho^{z_i} p^{y_i z_i / 2} (1 - p)^{(2 - y_i) z_i / 2} (1 - \rho)^{1 - z_i} \binom{2}{y_i} p^{y_i (1 - z_i)} (1 - p)^{(2 - y_i) (1 - z_i)}$$

The posterior distribution of  $(p, \rho)$  given  $(y, z)$ ,  $(y_0, z_0)$  and  $a_0$  is

$$P(p, \rho | | y, z, y_0, z_0, a_0) = P(y, z | p, \rho) P(y_0, z_0 | p, \rho)^{a_0} \pi_0(p, \rho)$$

where,  $\pi_0$  is joint prior distribution of  $(p, \rho)$ . Here we assume  $p$  and  $\rho$  to be independent with a prior beta  $(\alpha, \beta)$  for  $p$  and uniform  $(0,1)$  for  $\rho$ . Hence the joint distribution of  $(p, \rho)$  is given by  $\pi_0(p, \rho | \alpha, \beta) \propto p^{\alpha-1} (1-p)^{\beta-1}$ . The Metropolis sampler algorithm as implemented in the SAS/STAT MCMC Procedure will be used to estimate the posterior distributions of the parameters  $(p, \rho)$ . Inferences will be made based on a posterior credible interval for the relevant parameters.

## Hypothesis Testing

With respect to unacceptable lens fit the null and alternative hypothesis for superiority is as follows:

$$\begin{aligned} H_o &: p_T \geq 0.05 \\ H_A &: p_T < 0.05 \end{aligned}$$

Where,  $p_T$  represents the proportion of subject eyes that are considered to have unacceptable fit for the study lens after 2-weeks of lens wear. Success for unacceptable fit will be declared if the upper bound of the 2-sided 95% credible interval of the proportion is lower than 0.05; i.e.  $P(p_T < 0.05) \geq .975$ .

With respect to Grade 3 or Higher SLFs the null and alternative hypothesis for superiority is as follows:

$$H_o : p_T \geq 0.05$$

$$H_A : p_T < 0.05$$

Where,  $p_T$  represents the proportion of subject that experienced any Grade 3 or Higher SLF or experienced a corneal infiltrate. Success for Grade 3 or higher SLFs will be declared if the upper bound of the 2-sided 95% credible interval of the proportion is lower than 0.05; i.e.  $P(p_T < 0.05) \geq .975$ .

If no SLF findings of Grade 3 or higher or unacceptable lens fit is observed, alternative analysis methods may be considered.

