- Unacceptable Len Fit: The Null hypothesis will be rejected if the upper bound of the 2-sided 95% credible interval of the posterior estimate of the proportion of eyes with unacceptable lens fitting is below 5%.

If no SLF findings of Grade 3 or higher or unacceptable lens fit is observed, alternative analysis methods will be considered. More details will be provided in the statistical analysis plan.

Primary Efficacy Analyses:

Efficacy analysis will be conducted the Intent-to-Treat Population (ITT) without borrowing from historical data. A sensitivity analysis will be performed by incorporating historical historical data. The level of borrowing used in the safety analysis will be considered. Further sensitivity analyses on the Per-Protocol Population will also be considered.

CLUE Vision

CLUE vision scores will be analyzed using a Bayesian normal random effects model for repeated measures. The model will include baseline clue score, age, add power, gender, timepoint (3-day and 2-week follow-up evaluations) and strata (Hyperopes and Myopes) and the interaction between timepoint and strata as fixed effects. Site will be included as a random effect. An unstructured (UN) covariance structure will be used to model the residual errors from measurements within the same subject across timepoints. Heterogeneous residuals covariance structures (R-side) across strata will be considered when appropriate. Non-informative priors will be used for the unknown parameter. For the β coefficients, independent non-informative priors $N(0, 1000)$ will be used. For the variance of random effect σ_{site}^2 an independent non-informative conjugate prior inverse-gamma(0.001, 0.001) will be used. For the residual covariance structure an inverse-Wishart distribution will be used. Inferences will be carried out using the 95% posterior credible intervals for relevant parameters.

Hypothesis testing for CLUE Vision Scores endpoints will be conducted separately for each stratum:

- Hyperopes: The Null hypothesis will be rejected if the lower bound of the 2-sided 95% credible interval of the clue vision posterior mean estimate is above 32.
- Myopes: The Null hypothesis will be rejected if the lower bound of the 2-sided 95% credible interval of the clue vision posterior mean estimate is above 40.

Visual Acuity

Binocular high luminance, high contrast (HLHC) visual acuity (logMAR) at the 2-week follow-up evaluation will be analyzed using a Bayesian normal random-effects model for

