## 1. INTRODUCTION

This statistical analysis plan (SAP) describes the analyses and data presentations for protocol CR-6400 Version 4.0.

This document will serve as the final guidance for all the statistical analysis for this study and will supersede the Statistical Method section in the protocol if there are any discrepancies. Any deviation from the analysis plan will be documented as such in the clinical study report.

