### Unacceptable Lens Fit

Unacceptable lens fit will be assessed at all study visits (scheduled and unscheduled) for each subject eye. Unacceptable fit is a binary response where Y=1 if lens fit is unacceptable and

CR-6400, Statistical Analysis Plan Version 1.0

Y=0 otherwise. Unacceptable fit was defined as unacceptable if any one of the following criteria:

- limbal exposure at primary gaze or with extreme eye movement;
- edge lift;
- excessive movement in primary up gaze;
- insufficient movement in all three of the following conditions: primary gaze, up gaze, and push up test.

Eyes with multiple unacceptable fitting events was counted only once. See CTP-2008 in Appendix H for additional details regarding lens fit assessments.

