##### Primary Hypotheses:

1. After approximately 2-weeks of wear, the mean overall quality of vision score of the Test lenses will be statistically better than 40 points for the myope population. This will be recorded by the subject using the CLUE Follow-up Questionnaire.
2. After approximately 2-weeks of wear, the mean overall quality of vision score for the Test lenses will be statistically better than 32 points for the hyperope population. This will be recorded by the subject using the CLUE Follow-up Questionnaire.
3. After approximately 2-weeks of wear, the mean distance, binocular, high luminance, high contrast logMAR visual acuity score of the Test lens will be statistically lower than 0.10 logMAR.
4. After approximately 2-weeks of wear, the mean intermediate, binocular, high luminance, high contrast logMAR visual acuity score of the Test lens will be statistically lower than 0.17 logMAR.
5. After approximately 2-weeks of wear the mean near, binocular, high luminance, high contrast logMAR visual acuity score of the Test lens will be statistically lower than 0.17 logMAR.

**CR-6400**, Statistical Analysis Plan Version 1.0

6. When wearing the Test lenses, the proportion (%) of eyes with at least one reported clinically significant slit-lamp finding (Grade 3 or 4) during the post-fit period will be significantly lower than 5%.

7. When wearing the Test lenses, the proportion (%) of eyes with an unacceptable fit during the study will be statistically less than 5%.

If all the primary hypotheses are met, the following secondary hypothesis will be tested.

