### **8.2. Summary Statistics**

Throughout the analysis of data, the results for each subject/eye will be used when available for summarization and statistical analysis. Unscheduled visits will be summarized separately and will be excluded from the efficacy statistical analysis but will be included in the analysis of safety endpoints (slit lamp findings and lens fitting).

Summary tables (descriptive statistics and/or frequency tables) will be provided for all baseline variables, efficacy variables and safety variables as appropriate. Continuous variables will be summarized with descriptive statistics (n, mean, standard deviation [SD], median, minimum, and maximum). Frequency count and percentage of subjects or eyes within each category will be provided for categorical data.

Safety and efficacy variables will be summarized on both safety and PP populations.

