### **8.4. Sample Size Justification**

This study was designed and powered to demonstrate that the Multifocal Test lens made with senofilcon A material made from the Flexible Manufacturing Platform (FMP), in its final lens design FAL100, FAL101 and FAL102 (low, mid and high ADD respectively) meets the design validation requirements for the following efficacy and safety endpoints:

- CLUE vision score at 2-week follow-up
- Binocular visual acuity (Distance, Intermediate and Near) at 2-week follow-up
- Proportion of eyes with a significant slit lamp finding (Grade 3 or higher)
- Proportion of eyes with unacceptable lens fitting

The historical data used for the sample size calculation were from 6 JJVC sponsored studies. Table 4 displays the studies, their corresponding study design and the number of subjects enrolled and

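### SAP 11.1 defines the co-primary lens-fit parameter at 2 weeks, although the endpoint, the hypothesis and the rest of the SAP count unacceptable fit at any visit

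*SAP*

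**What the plan says.** SAP 11.1, Hypothesis Testing, states that the fit parameter p_T "represents the proportion of subject eyes that are considered to have unacceptable fit for the study lens after 2-weeks of lens wear". Success requires the upper bound of the two-sided 95% credible interval to lie below 0.05, that is, P(p_T < 0.05) of at least 0.975.

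Elsewhere the SAP describes a different quantity:

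- SAP 4: "Unacceptable lens fit will be assessed at all study visits (scheduled and unscheduled) for each subject eye", and "Eyes with multiple unacceptable fitting events was counted only once".
- SAP 5.1, hypothesis 7: "the proportion (%) of eyes with an unacceptable fit during the study will be statistically less than 5" per cent.
- SAP 8.2: unscheduled visits "will be included in the analysis of safety endpoints (slit lamp findings and lens fitting").
- SAP 8.4 ties CLUE and visual acuity to the 2-week follow-up, but lists fit simply as "Proportion of eyes with unacceptable lens fitting".
- SAP 11.1 runs the fit analysis on the safety population, which under SAP 6.3 keeps subjects who stop early.

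The protocol agrees with the any-visit version. Sections 2.2 and 2.3 carry the same endpoint and hypothesis, and the test in 14.5 is on the upper bound "of the posterior estimate of the proportion of eyes with unacceptable lens fitting is below 5" per cent, with no time restriction.

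**The concern.** Fit is one of seven co-primary hypotheses, all of which must be met. Protocol steps 1.27 and 2.10 (Section 7.2) and U.8 (Section 7.3) discontinue a subject when either lens is judged unacceptable. A subject who fails at Visit 1, Visit 2 or an unscheduled visit before Visit 3 therefore has no 2-week fit value. SAP 8.6 does not impute in the main analysis; Bayesian imputation is planned only as a sensitivity analysis. Under the literal 2-week definition these subjects drop out of the test because of the very event being tested.

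The code in SAP 14.2.1 takes y as given and does not state which visits feed it. Two programmers could build two different outcomes, each able to cite the SAP, and the choice could be made after the data are known.

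**Working it through.** **Inputs.** Decision rule: P(p<0.05) ≥ 0.975 (SAP 11.1). Model: the two-eye mixture of SAP 11.1, with p ~ Beta(0.5, 0.5) and ρ ~ Uniform(0, 1) (SAP 14.2.1). Borrowing: weight 0.3 for 23 + 66 subjects and 0.1 for 86 (SAP Table 7), so 0.3 × 89 + 0.1 × 86 = 26.7 + 8.6 = 35.3 effective historical subjects. Historical events: one eye in 350 (SAP Table 6). Its platform is not given, so ranges show it at weight 0.3 and at 0.1. Planning values: p = 0.01, ρ = 0.80 (SAP 8.4).

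**Formulas.** For a subject with Y unacceptable eyes:

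- P(Y=0) = (1−ρ)(1−p)² + ρ(1−p)
- P(Y=1) = 2(1−ρ)p(1−p)
- P(Y=2) = (1−ρ)p² + ρp

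The posterior is the prior, times the current likelihood, times each historical likelihood raised to its weight. It was evaluated on a grid.

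**The plan's own figure.** SAP Table 8 gives 90% power for fit with 60 subjects. The rule as written gives 85.2%; a highest-density interval or a one-sided 95% bound gives 90.9%. The model is therefore close to the one used, and nothing below depends on the gap.

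**Effect of dropping one early failure.** Two subjects fail in both eyes:

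| Fitted | All visits counted | One of the two early and dropped |
|---|---|---|
| 60 | 0.939–0.947 (fail) | 0.987–0.990 (pass) |
| 70 | 0.960–0.966 (fail) | 0.992–0.994 (pass) |
| 80 | 0.9745–0.978 (borderline) | 0.996 (pass) |

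**Effect of losing other subjects.** A 2-week count also omits everyone who leaves before Visit 3 for reasons other than fit. Take 80 fitted, two bilateral failures both found at Visit 3, and 20 others lost. The all-visit count keeps 80 subjects: 0.9745–0.978, borderline. The 2-week count keeps 60: 0.939–0.947, a fail. This pulls in the opposite direction.

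**Both effects together.** Simulated pass rates with 80 fitted, ρ = 0.8, the historical event at weight 0.3, and 25% lost before Visit 3 for other reasons. That 25% is an assumption taken from 80 enrolled and 60 completing, (80 − 60)/80; some of the 80 may be screen failures. The early share is the assumed proportion of fit failures occurring before Visit 3.

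| Early share | True 1%: all-visit v 2-week | True 5%: all-visit v 2-week |
|---|---|---|
| 10% | about 91% v 89% | about 28% v 21% |
| 25% | about 90% v 91% | about 22% v 28% |
| 50% | about 89% v 96% | about 20% v 49% |

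Repeat runs move these by up to about three points. The all-visit column falls as the early share rises because late failures in subjects already lost are never observed, whereas early ones are.

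The all-visit pass rate at a true 5% is well above 2.5% mainly because of borrowing: with 60 fitted and no other loss it is about 14% with borrowing and 5% without. That is not caused by the definition at issue here.

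**The case against.** The best defence is that the documents already settle the intent. Apart from the one sentence in SAP 11.1, the SAP text on this endpoint and its analysis points to any-visit counting; counting an eye only once means little if a single visit is analysed; and dropping early failures sits badly with a safety-population analysis. The sentence may be loose wording for the period of 2 weeks' wear. Early failures would also stay visible: Protocol 8.2 has discontinued subjects complete the current visit, and SAP 12.4 tabulates discontinuations by visit with unsatisfactory fit as a reason. All of this stands, and it makes the point a wording repair and not a design flaw. It does not remove the point, because the outlier is the decision-defining sentence and the code leaves the visit rule open.

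Two stronger readings are tempting and are not supported.

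- A reader might infer that the 2-week definition can only make success easier. It removes early failures, which does favour success, but it also removes subjects lost for other reasons, which does not. At a 10% early share the literal reading is the harder test.
- A reader might infer that the 2-week definition governs because the SAP "will supersede the Statistical Method section in the protocol if there are any discrepancies". That clause ranks the SAP over the protocol's statistical section only. It does not rank SAP 11.1 over SAP 4 or 5.1, and the any-visit endpoint and hypothesis also stand in Protocol 2.2 and 2.3, outside that section.

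**Conclusion.** The inconsistency is real and lies within the SAP. It should be corrected before the analysis dataset is built. Any-visit is the evident intent.

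If the sentence were followed literally, a single early failure could turn a fail into a pass. Across a whole trial, the net effect could go either way. At the planned 1% rate it is small for early shares of 10% to 25% and about seven points in favour of passing at 50% (89% v 96%). At a true rate on the 5% limit it runs from about seven points against passing (28% v 21%) to about 29 points in favour (20% v 49%).

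These figures rest on assumptions the documents do not supply: the number fitted, the early share, the 25% loss for other reasons, and discontinuation of every early failure. An eye that met an endpoint criterion but not the listed stop rule could reach Visit 3, which would lessen the effect.

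**What to change.** In SAP 11.1, replace the fit definition with: *p_T is the proportion of eyes in the safety population with an unacceptable lens fit at any scheduled or unscheduled visit, each eye counted once.* In SAP 14.2, state that y is built by the same rule.

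As a wording correction in the same section, the slit-lamp definition should refer to the proportion of subject eyes, since the model and hypothesis 6 are per eye.

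The cost is two edited sentences and one line in the code appendix. No new data are needed, because fit failures are recorded at the visit where they occur.

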2.10	Lens Fit Assessment	
Evaluate and grade lens centration, primary gaze movement, upgaze movement and tightness (push-up test).
 
 • The subject should not proceed to wear the lenses if any of the following is observed: • presence of limbal exposure (appearance of clear cornea) in any gaze • presence of edge lift • presence of unacceptable movement (excessive or insufficient) in all three movement categories (primary gaze, upgaze, and push-up). 
If either lens is deemed unacceptable, the subject will be discontinued from the study. Remove the lenses, perform a slit-lamp evaluation, and complete the Final Evaluation form.
	
2.12	Lens Removal	The study lenses will be removed and discarded.	
2.13	Biomicroscopy	
Perform Biomicroscopy OD and OS. FDA Slit Lamp Classification Scales* will be used to grade the findings.
 
*note: for corneal staining note location (nasal, temporal, superior, inferior or central)
	

Clinical Study Protocol
Johnson & Johnson Vision Care, Inc.

		
If any of these slit lamp findings are Grade 3 or higher, an AE must be recorded. All AEs must be followed to resolution. After resolution the subject will be discontinued and Final evaluation completed.
 
If the clearance of the fluorescein needs to be expedited, preservative-free rewetting drops may be instilled.
	
2.14	Insertion of Study Lenses	Dispense the subject a new pair of lenses that match the distance and ADD power of the lenses that were removed in Step 2.12 above.	
2.15	PRO (MRD) Questionnaire	The subject will evaluate the vision characteristics, comfort characteristics, handling characteristics, and visual symptoms of the study lenses using the PRO questionnaire.	
2.16	Distance and Near Exit Visual Acuity	
Distance and near Snellen visual acuity will be measured for each eye with the study contact lenses in place.
 
For near measures use the ETDRS 2000 Series Chart 1 or 2.
 
The acuity will be recorded to the nearest letter OD, OS and OU.
 
Note: The distance visual acuity must be at least 20/30 OU for the lenses to be dispensed.
	
2.17	Dispensing Criteria	
The lenses will be dispensed for 10-14 days.
 
 • Distance Snellen acuity equal to or better than 20/30 OU • Subject must indicate that the vision is acceptable. • Subject must indicate that the comfort of the lenses is acceptable. • Lenses must have an acceptable general lens fit. 	

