### **6.3. Safety Population**

All subjects who were administered any test article with at least one observation recorded excluding subjects who dropped out prior administering any test article. Safety analyses will be based on the safety population.

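### SAP 11.1 ties the unacceptable-fit co-primary to two weeks of wear, while the rest of the SAP counts failures at any visit; the 11.1 phrase should be corrected (minor)

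*SAP*

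**What the plan says.** **Time window.** In SAP 11.1 (Hypothesis Testing), p_T for fit is the proportion of eyes "considered to have unacceptable fit for the study lens after 2-weeks of lens wear". Success requires P(p_T < 0.05) of at least 0.975.

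Elsewhere in the SAP:
- SAP 4: "Unacceptable lens fit will be assessed at all study visits (scheduled and unscheduled) for each" subject eye. An eye with several events counts once.
- SAP 5.1, hypothesis 7: the proportion "of eyes with an unacceptable fit during the study will be statistically less than 5" per cent.
- SAP 8.2: unscheduled visits "will be included in the analysis of safety endpoints (slit lamp findings and lens fitting").
- SAP 6.3 defines the population for the safety analyses: "All subjects who were administered any test article with at least one observation recorded".

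Protocol 2.2, 2.3 and 14.1 match SAP 4, 5.1 and 8.2. SAP 1 says that the SAP "will supersede the Statistical Method section in the protocol if there are any discrepancies"; it sets no order among the SAP's own sections.

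**Consequence of an early failure.** Protocol 7.2, steps 1.27 and 2.10: "If either lens is deemed unacceptable, the subject will be discontinued from the study".

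**Movement criterion.** SAP 4 and Protocol 2.2 fail an eye for "excessive movement in primary up gaze". CTP-2008 (Protocol Appendix H) grades primary gaze and upgaze on separate scales. Its fit table uses grade +2 in primary gaze.

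**The concern.** Section 11.1 is where the tested parameter is written down, so a programmer may well work from it. The conflict lies inside the SAP, and the precedence rule in SAP 1 does not resolve it.

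The phrase also has a direction. A subject whose lens fails fit at Visit 1 or 2 has worn a test lens and has an observation, so belongs to the safety population, but leaves before the 2-week visit. A literal 2-week window drops both eyes of that subject from numerator and denominator. The failures serious enough to stop wear would then not count. Fit is one of seven co-primary hypotheses that must all be met, and its pass limit is two or three eyes, so a single bilateral failure can decide it.

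**Working it through.** **Inputs.** Priors p ~ Beta(0.5, 0.5) and ρ ~ U(0, 1) (SAP 14.2.1). Borrowing weights 0.3 for 23 + 66 = 89 subjects and 0.1 for 86 (SAP Table 7), so 0.3 × 89 + 0.1 × 86 = 35.3 effective historical subjects. One historical affected eye in 350 (SAP Table 6); its platform is not given, so both placements were run. Planning values p = 0.01 and ρ = 0.80 (SAP 8.4).

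**Model** (SAP 11.1), affected eyes per subject:
- P(0) = (1−ρ)(1−p)² + ρ(1−p)
- P(1) = 2(1−ρ)p(1−p)
- P(2) = (1−ρ)p² + ρp

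At the planning values these are 0.98802, 0.00396 and 0.00802. The posterior was integrated on a grid.

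**The plan's own figure.** SAP Table 8 gives 90% power for fit at 60 subjects. Under the stated rule, the passing outcomes are no affected eye, one affected subject, or two unilateral subjects:

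0.98802⁶⁰ + 60 × 0.98802⁵⁹ × 0.01198 + 1770 × 0.98802⁵⁸ × 0.00396² = 0.485 + 0.353 + 0.014 = 0.852.

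A highest-density 95% interval gives 0.909, which matches the table. What follows uses the rule SAP 11.1 states, P ≥ 0.975.

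**Pass limit.** Ranges cover both placements of the historical eye and unilateral or bilateral failures.

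| Subjects | Affected eyes | P(p < 0.05) | Result |
|---|---|---|---|
| 60 | 2 | 0.988–0.990 | pass |
| 60 | 3 | 0.969–0.974 | fail |
| 66 | 3 | 0.977–0.982 | pass |
| 66 | 4 | 0.951–0.959 | fail |

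The second size allows for dropouts, who remain in the safety population: 60/(411/454) = 66.3, applying the historical completion rate in SAP Table 4.

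**Example at 66 subjects.** Two subjects fail bilaterally at Visit 1 or 2 and nobody else fails. Counting any visit gives 4/132 eyes and P = 0.953–0.959, a fail. The literal window leaves 64 subjects, 0/128 eyes and P = 0.999, a pass.

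**How often the two readings disagree.** Let each affected subject be stopped before the 2-week visit with probability f and then be absent from the literal analysis. All outcomes were enumerated at ρ = 0.80. Probability that the literal window passes and any-visit fails:

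| True rate | Subjects | f = 0.25 | f = 0.50 |
|---|---|---|---|
| 0.01 (planning) | 60 | 0.056 | 0.102 |
| 0.01 (planning) | 66 | 0.042–0.043 | 0.076–0.077 |
| 1/350 (historical) | 60 | 0.007 | 0.012 |
| 1/350 (historical) | 66 | 0.004 | 0.008 |

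**Movement criterion.** The visit steps record primary gaze, upgaze and push-up, with no combined position. The phrase could be coded as primary gaze, upgaze or either. CTP-2008 notes for both gaze scales that +2 movement typically exposes the limbus, and limbal exposure already fails the eye under SAP 4.

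**The case against.** The strongest reply is that the documents already settle the window. The endpoint definition, the hypothesis, the rule on unscheduled visits and the choice of analysis population all point to any visit, and counting an eye once despite several events presupposes pooling across visits. One explanatory clause stands against them. It can even be read as status accumulated by the end of roughly two weeks of wear. This largely stands, and it is why the point is minor.

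A reader might infer that the sponsor intends a 2-week-only endpoint, or that the planned test is biased toward success. The documents do not support either. The bias appears only if an analyst follows the 11.1 clause and sets the endpoint definition aside. SAP 12.8 does tabulate fit characteristics at fitting and 2 weeks only, but that table is descriptive and does not define the co-primary.

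The size is also open to challenge, with some force. No source gives the share stopped early. At the historical rate the disagreement is about a tenth of that at the planning rate. The 66 subjects rest on a completion rate whose enrolled count may include people never dispensed lenses. The worked example needs two early bilateral failures, while the historical data hold one affected eye in all.

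On the gaze wording, a reader might infer that the endpoint cannot be scored. That goes too far: SAP 4 refers to CTP-2008, and all the grades are collected.

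**Conclusion.** SAP 11.1 is wrong as written on the window; severity is minor. Any-visit counting is the evident intent, and the literal phrase conflicts with it in the direction of success. If it were followed, the result would change with probability about 0.04–0.10 at p = 0.01, or about 0.004–0.012 at 1/350. Those figures rest on 60 to 66 subjects, ρ = 0.80 and an assumed quarter to a half of failing subjects stopped before the 2-week visit. The direction needs none of these assumptions.

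The movement phrase is a near-clerical slip that probably changes few eyes. The documents do not say how often primary-gaze and upgaze grades differ.

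**What to change.** In SAP 11.1, replace the 2-week restriction in the definition of p_T for fit with *at any scheduled or unscheduled visit during the study*, and state that the analysis is on the safety population.

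As a minor companion edit, state the excessive-movement criterion in SAP 4 as a graded position. Grade +2 in primary gaze, the CTP-2008 guideline, is the natural default. CTP-2008 lets the protocol set its own determinants, so use another position if the borrowed historical eyes were scored that way.

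Both are wording changes to make before database lock. They need no new data, because fit is already graded at every visit. Protocol 2.2 carries the same gaze phrase and lies outside the section the SAP supersedes; it can be aligned if the protocol is next revised.
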